4.6.2.1. Safety Run-in and Part 2, Arm A (Plamotamab, Tafasitamab and Lenalidomide)

Infusion-related reactions have been observed with plamotamab and tafasitamab. To mitigate overlapping toxicity with plamotamab, on a given treatment day, tafasitamab must be given first with a minimum of 2 hours between the end of the tafasitamab infusion and the start of the plamotamab infusion. If a > Grade 1 infusion reaction occurs with tafasitamab, delay the plamotamab until the resolution all symptoms of the reaction. Depending on the timing of the resolution of all symptoms, it may be necessary to administer the plamotamab the following day.

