		
on the C1D1 dose, in which case 100% of the previous dose may be given.
 
 • For subsequent plamotamab infusions, if: 
 – Toxicity does not recur or recurs at a Grade 1 severity, escalate to full dose of plamotamab at the time of the next dose. – Toxicity recurs at a Grade 2 severity, maintain 75% dosing of plamotamab. – Toxicity recurs at \geq Grade 3 severity at any time or if a Grade 2 takes more than 10 days to resolve to \leq Grade 1, discontinue plamotamab permanently. • Lenalidomide is also modified if a \geq Grade 3 CRS event occurs: 
 – During the first 5 doses of plamotamab: Reduce current dose of lenalidomide by 10 mg (or to 5 mg if currently at 10 mg) for subsequent doses until C4D1, when lenalidomide may be increased back to the dose prior to CRS. If CRS recurs at \geq Grade 2 on subsequent reduced dose lenalidomide, permanently discontinue lenalidomide. – After the first 5 doses of plamotamab: Reduce lenalidomide by 10 mg (or to 5 mg if currently at 10 mg) for all subsequent doses. If CRS recurs at \geq Grade 2 on subsequent reduced dose lenalidomide, permanently discontinue lenalidomide. • Tafasitamab dose is not modified.
Myelosuppression	Platelet count of less than 50,000/ μ L	
 • Withhold plamotamab, tafasitamab, and lenalidomide and monitor CBC weekly until platelet count is 50,000/μL or higher. • Resume plamotamab and tafasitamab at the same dose and lenalidomide at a reduced dose. Refer to lenalidomide prescribing information for dosage modifications. • If recurrence, repeat drug withholding and lenalidomide reduction steps until minimal lenalidomide dose is reached per lenalidomide prescribing information. • If recurrence at minimal lenalidomide dose, repeat drug withholding step (first bullet above) then reduce the next scheduled plamotamab dose to 75% of the previous dose.

Adverse Reaction	Severity	Dosage Modification

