	
Neutrophil count of 1,000/μL or less for at least 7 days OR
 
Neutrophil count of 1,000/μL or less with an increase of body temperature to 100.4°F (38°C) or higher OR
 
Neutrophil count less than 500/μL
	
 • Withhold plamotamab, tafasitamab, and lenalidomide and monitor CBC weekly until neutrophil count is 1,000/μL or higher. • Resume plamotamab and tafasitamab at the same dose and lenalidomide at a reduced dose. Refer to lenalidomide prescribing information for dosage modifications. • If recurrence, repeat drug withholding (first bullet above) and lenalidomide reduction steps until minimal lenalidomide dose is reached per lenalidomide prescribing information. • If recurrence at 5 mg lenalidomide, repeat drug withholding steps then reduce the next scheduled plamotamab dose to 75% of the previous dose.
Febrile Neutropenia	Grade 3 (severe) & Grade 4 (life-threatening)	
 • Withhold plamotamab, tafasitamab, and lenalidomide and monitor CBC until neutrophil count is Grade \leq 1. • Once subject is afebrile, off antibiotics and neutrophil count is Grade \leq 1, resume all therapy at the same dose and schedule.
Neurotoxicity	Grade 3 (severe)	
 • Withhold plamotamab and manage signs and symptoms (see Section 4.6.1.7) until the toxicity has recovered to \leq Grade 1 (mild) and has remained at \leq Grade 1 for at least 3 days before restarting therapy. • Reduce next scheduled plamotamab dose to 75% of the previous dose. If \geq Grade 2 toxicity does not recur, escalate plamotamab to full dose in subsequent administrations. • If \geq Grade 2 toxicity recurs at 75% dose, or if $<$ Grade 2 toxicity takes more than 7 days to resolve, permanently discontinue plamotamab. • Tafasitamab and lenalidomide dosing is not modified.
	Grade 4 (life-threatening)	
 • Stop infusion immediately, if still infusing and permanently discontinue plamotamab.
AST, ALT, bilirubin, and alkaline phosphatase in the absence of CRS	Grade 3 (severe)	
 • Withhold plamotamab and manage signs and symptoms until the toxicity has recovered to \leq Grade 1 (mild) or baseline. • If a Grade 3 liver toxicity persists $>$ 14 days and/or 2 consecutive doses are missed and the toxicity cannot be attributed to another cause, permanently discontinue plamotamab. • Tafasitamab and lenalidomide dosing is not modified.

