- ^c For subjects who tolerate 4 consecutive infusions of plamotamab at a stable dose and schedule without CRS or an infusion reaction during the infusion or post-infusion observation period, the post-infusion observation period and vital signs assessment may be reduced from 5 hours to 2 hours.
- ^d Tafasitamab is administered as a 2 hour IV infusion. On days when both plamotamab and tafasitamab are given, the tafasitamab should be administered before plamotamab with at least 2 hours between the infusions.
- ^e Lenalidomide is administered orally once daily in the evening on Days 1 to 21 of each 28-day cycle, up to 12 cycles.
- ^f Complete medical history and PE is required at screening. For all the other time points an abbreviated, symptom-directed PE is to be performed.
- ^g May be performed the day prior to the plamotamab infusion. Results should be available and reviewed before starting plamotamab infusion.
- ^h ASTCT ICANS Consensus Grading for Adults, [Table 5](#) and [Table 6](#), must be completed at least 1 hour post-infusion, but no more than 12 hours post-infusion, on the day of plamotamab infusion. On days when no study drug infusion occurs, the assessments should be completed at approximately the same time each day (approximately 24 hours post-infusion, 48 hours post-infusion, 72 hours post-infusion, etc.). Beginning with Cycle 4, the ASTCT ICANS Consensus Grading assessments are only required on Day 1 of subsequent cycles. ICANS Grading should also be performed if clinically indicated.

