- ⁱ Supine or sitting blood pressure and heart rate, body temperature, respiratory rate, and blood oxygen saturation by continuous pulse oximetry. On days of infusions, vital signs coinciding with the plamotamab dosing should be taken predose; 15, 30, and 60 minutes after start of infusion (± 5 minutes); at EOI (± 5 minutes); 15 (± 5 minutes); 30 (± 5 minutes); and 60 (± 10 minutes) minutes after EOI; and then hourly for 4 hours (± 15 minutes). Vital signs for the tafasitamab dosing should be taken predose and 30 minutes after EOI (± 5 minutes). All vital signs during infusion should be taken with subject in the same position. The pulse oximetry for blood oxygen saturation level needs to be captured with each vital sign collection; however, pulse oximetry monitoring must be maintained continuously, as practical, throughout the entire admission period for each administration of plamotamab, regardless of inpatient or outpatient status. For more information of management of oxygen saturation of 90% or lower, see [Section 4.6.1.4](#).
- ^j If performed on dosing days, the assessment should be performed prior to administration of any study drug.
- ^k Urinalysis is required; the microscopy is only required if clinically indicated.
- ^l May be performed up to 8 weeks prior to screening.
- ^m HBsAg and Hepatitis B DNA repeat testing should be performed only if HBcAb serology is positive and HBsAb serology is negative at screening. Testing for visit Days 1 at Cycle 2 and subsequent cycles should be done 1 to 3 days prior to the Day 1 visit so that results are available prior to the Day 1 dose for the subsequent cycles.
- ⁿ FSH needs only to be performed at screening for suspected postmenopausal women. If menstrual cycles are irregular, the pregnancy testing should occur every 2 weeks.
- ^o Draw prior to study drug administration. In addition, unscheduled samples, if available, may be sent to the designated central laboratory per the laboratory manual for flow and biomarker analysis. The frequency of biomarker collections may be reduced during the study based on emerging data.
- ^p SARS-CoV-2 nucleic acid or antigen test, performed locally, is to be completed and result within 7 days prior to Day -8.

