7.5.1. Screening Evaluations (Up to Day –35)

In Part 1, screening assessments are to be performed during the 28-day window prior to the priming dose of tafasitamab. In Part 2, screening assessments are to be performed within 28 days of randomization.

- Obtain signed informed consent (may be done up to Day –35)
- Review inclusion and exclusion criteria
- Medical history and physical exam (PE)
- Neurologic examination will be assessed using the ASTCT ICANS Consensus Grading for Adults (see [Section 4.6.1.7](#))

- Any cytogenetic information available on the tumor from time of original diagnosis and at transformation (if applicable) should be recorded, including cytogenetics, fluorescent in situ hybridization (FISH) analysis, and sequencing data
- Vital signs (supine or sitting position, including heart rate, blood pressure, temperature, respiratory rate, and blood oxygen saturation by pulse oximetry)
- Height, weight
- ECOG performance status (see [Appendix A](#), Performance Status Scale)
- Electrocardiogram (ECG), standard 12-lead, supine position
- Complete blood count (CBC): RBC, hemoglobin, hematocrit, mean corpuscular volume (MCV), RBC distribution width (RDW), white blood cell (WBC) with differential (neutrophils, lymphocytes, monocytes, eosinophils, basophils, myelocytes, promyelocytes; include percent and absolute, if reported) and platelet count
- Chemistry panel (sodium, chloride, potassium, bicarbonate, blood urea nitrogen, creatinine, glucose, uric acid, calcium, phosphorous, total bilirubin, ALT, AST, total protein, albumin, alkaline phosphatase, LDH, as well as serum gamma-glutamyl transferase [GGT], amylase, lipase, ferritin (screening only), and C-reactive protein (screening only))
- Coagulation panel (prothrombin time [PT]/international normalized ratio [INR] and activated partial thromboplastin time [APTT])
- Urinalysis with microscopy (pH, specific gravity, ketones, leukocyte esterase, bilirubin, blood, and protein; microscopy may include RBCs, WBCs, hyaline casts, RBC casts, WBC casts, granular casts, waxy casts [include microscopy findings in EDC only if reported])
- Hepatitis B (HBsAg, HBcAb, and HBsAb) and C (HCV), and HIV screening. These tests may have been performed within the previous 8 weeks.
- If HBcAb or HBsAg is positive, perform hepatitis B DNA testing. If subject is negative, subject may be enrolled if hepatitis B reactivation prophylaxis is initiated with entecavir, tenofovir, or lamivudine

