7.5.2. Day –8, Day –4, and Day –1

- Abbreviated PE (Day –8 and Day –1 only)
- Neurologic examination will be assessed using the ASTCT ICANS Consensus Grading for Adults (Day –1 only, see [Section 4.6.1.7](#))

- Vital signs (supine or sitting position, including heart rate, blood pressure, temperature, respiratory rate, and blood oxygen saturation by continuous pulse oximetry)
- Weight (Day –8 and Day –1)
- ECOG performance status (see [Appendix A](#))
- CBC with differential (percent and absolute) and platelet count (see [Section 7.5.1](#)) (Day –8 and Day –1 only)
- Chemistry panel (see [Section 7.5.1](#)) (Day –8 and Day –1 only)
- Fibrinogen (Day –1 only)
- Coagulation panel (PT/ INR and APTT) (Day –1 only)
- Urinalysis (see [Section 7.5.1](#)) (Day –8 and Day –1 only)
- Urine or serum β -hCG pregnancy test for women of childbearing potential (Day –8 and Day -1 only)
- The following to be sent to the central laboratory per the laboratory manual:
 - Serum sample for rituximab level (Day –1 only)
 - Serum samples for tafasitamab PK and ADA (Day –8 only)
 - Peripheral blood for TBNK, leukocyte flow cytometry (Day –8 only)
 - Peripheral blood for RNA analysis (Day –8 only, prior to tafasitamab dose)
- Administration of tafasitamab on Day –8 and Day –4
- Record concomitant medications and AEs

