Laboratory Assessments: Safety laboratory assessments, including CBC with differential, chemistry panel, fibrinogen, coagulation panel, urinalysis, and pregnancy tests, may be completed up to 24 hours prior to the visit day. Excepted is the pregnancy test prior to the first dose of lenalidomide, which should be completed on Cycle 1 Day 1, within 24 hours of initiating treatment. Safety laboratory values, except for differential counts, fibrinogen, coagulation panel, and urinalysis, should be reviewed before starting study drug infusion.

- CBC with differential (absolute and percent), platelet count, and blast count, if reported (see [Section 7.5.1](#))
- Chemistry panel (see [Section 7.5.1](#))
- Fibrinogen
- If HBcAb serology is positive, HBsAg and hepatitis B DNA testing should be performed, with results available prior to dosing, on Day 1 of Cycles 2 and later, and at EOT (unless HBsAb is also present).
- Coagulation panel (prothrombin time PT/INR and APTT)
- Urinalysis (see [Section 7.5.1](#))
- Urine or serum β -hCG pregnancy test for women of childbearing potential should occur weekly during the first 4 weeks of lenalidomide, then on Day 1 of each subsequent cycles for dosing of plamotamab, tafasitamab, or lenalidomide. If menstrual cycles are irregular, the pregnancy testing should occur every 2 weeks during each subsequent cycle.
- The following are to be sent to the central laboratory per the laboratory manual:
 - Serum samples for plamotamab and tafasitamab ADA, cytokines, and plamotamab and tafasitamab PK (see [Table 10](#) and [Table 11](#) for collection schedule). All samples should be drawn within the window indicated on [Table 9](#) and of the designated time and should be labeled with the exact, actual time of sampling.
 - Peripheral blood for TBNK, leukocyte flow cytometry
 - Peripheral blood for RNA analysis

- Peripheral blood for ctDNA analysis
- Tumor biopsies (for those subjects who provided consent) collected once at follow-up (See [Section 8.2.2](#) and [Table 9](#))

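### Section 7.6.1 exempts the neutrophil count from pre-infusion review although Table 8 withholds all three drugs on it, so the protocol's own text has no routine rule to read it before tafasitamab

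*Protocol*

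**What the plan says.** - **Review rule.** Section 7.6.1 (Laboratory Assessments): "Safety laboratory values, except for differential counts, fibrinogen, coagulation panel, and urinalysis, should be reviewed before starting study drug infusion".
- **Where neutrophils sit.** The CBC definition in Section 7.5.1 reads "white blood cell (WBC) with differential (neutrophils, lymphocytes, monocytes, eosinophils, basophils". The schedule has no separate neutrophil test.
- **Hold rules.** Table 8 in Section 4.7 says for neutrophils "Withhold plamotamab, tafasitamab, and lenalidomide and monitor CBC weekly until neutrophil count is" at least 1,000/µL, and for platelets "Withhold plamotamab, tafasitamab, and lenalidomide and monitor CBC weekly until platelet count is" at least 50,000/µL.
- **Table 9, footnote g**, on most on-treatment CBC cells: "May be performed the day prior to the plamotamab infusion. Results should be available and reviewed before starting plamotamab infusion".
- **Table 9, footnote j**, on the CBC row for pretreatment and Cycles 1 and 2: "If performed on dosing days, the assessment should be performed prior to administration of any study drug".
- **Order of infusions.** Section 4.6.2.1 says that on a shared day "tafasitamab must be given first with a minimum of 2 hours between the end of the tafasitamab infusion" and the start of plamotamab.
- **Before Cycle 1.** Section 7.5.2 schedules "CBC with differential (percent and absolute) and platelet count" on Day -8 and Day -1 only.

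**The concern.** A hold can act only on a value that someone has read. Section 7.6.1 tells sites that the differential need not be seen before they start an infusion, and the differential contains the count on which Table 8 stops all three drugs. Platelets, with the same three-drug hold, must be seen first. The protocol gives no reason for treating the two counts differently.

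The exempt count is also the one more often affected. Table 7 reports neutropenia of any grade in 51% with tafasitamab and lenalidomide, against 31% for thrombocytopenia. Section 4.6.3 warns that both may worsen in combination. Section 6.1 admits subjects with marrow involvement at a neutrophil count of 0.5 × 10⁹/L, which is 500/µL, right at the lowest Table 8 threshold.

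At stake is a tafasitamab infusion started, in full compliance with the protocol, while an unread result already meets a hold criterion.

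**Working it through.** The plan states no figure to reproduce. The check sets the texts side by side and then counts infusions in Table 9.

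**Does another text supply the missing rule?**
- Footnote g is stricter than 7.6.1, and a site can follow both, but it is tied to plamotamab. On shared days a site can comply with g after tafasitamab has been infused.
- Footnote j governs when the sample is taken, not when the result is read, and it is not marked on the CBC row from Cycle 3 onward.
- Section 4.6.3 asks for careful monitoring of blood counts but sets no pre-infusion step.
- Section 4.6.4.2 asks for real-time evaluation, but it concerns tumor lysis and names uric acid, potassium, phosphorus, calcium and creatinine.
- Section 7.4 requires review of screening data, which include the neutrophil criterion, once before treatment or randomization.
- Table 8 makes restart after a neutropenia or febrile neutropenia hold depend on the count. Those restarts are covered.

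**Count for Part 1 and Arm A, subject not on a hold (Table 9)**

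Tafasitamab infusions in Cycles 1 to 3: 3 × 4 = 12, each with a CBC scheduled that day. CBC cells carrying g: 3 (Cycle 1) + 4 (Cycle 2) + 4 (Cycle 3) = 11; Cycle 1 Day 1 has none. Plamotamab days: 4 + 4 + 2 = 10, of which 9 carry g. Cycles 4 to 12 add 9 × 2 = 18 tafasitamab infusions, all on shared days with g.

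| Situation | Cycles 1–3 | Cycles 4–12 | Through Cycle 12 |
|---|---|---|---|
| g marked, plamotamab given after tafasitamab | 9 | 18 | 27 |
| g marked, no plamotamab that day (Cycle 3 Days 8 and 22) | 2 | 0 | 2 |
| No g (Cycle 1 Day 1) | 1 | 0 | 1 |
| Total | 12 | 18 | 30 |

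Section 7.1.1 states every-2-week plamotamab from Cycle 2, whereas Table 9 shows weekly dosing in that cycle. Under 7.1.1, plamotamab days in Cycles 1 to 3 are 4 + 2 + 2 = 8, of which 7 carry g. The split becomes 7 + 4 + 1, and the total is still 12.

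**Arm B.** The same 12 and 30 infusions, none with plamotamab for g to precede.

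**Not counted.** The Day -8 and Day -4 priming doses fall under Section 7.5.2, outside 7.6.1.

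**How late can review under g come?** Section 7.1.2 gives 1.5 to 2 h for tafasitamab infusions after the first. With the 2 h gap of Section 4.6.2.1, plamotamab starts at least 1.5 + 2 = 3.5 h to 2 + 2 = 4 h after tafasitamab starts. The Synopsis and Section 4.3.1 only recommend that gap. Without it the interval could be as short as the 1.5 to 2 h infusion itself, but review under g could still follow tafasitamab.

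**Which Table 8 neutrophil triggers are exposed?** There are three. A count below 500/µL turns on one value. A count of 1,000/µL or less with a temperature of 38 °C or higher can be met by one count plus the predose temperature. A count of 1,000/µL or less for at least 7 days needs earlier counts as well.

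**The case against.** **Restart after a hold.** A reader might infer that nothing in the protocol ever requires the count before tafasitamab. The documents do not support that: under both the neutropenia and febrile neutropenia rows of Table 8, tafasitamab cannot resume until the count has recovered. The counts above therefore apply only to subjects not on a hold.

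**Prescribing information.** Sections 2.4.3, 7.1.2 and 7.10.2 have tafasitamab given according to its label, and Section 4.6.3.2 sends Arm B there for hematologic toxicity. The label may contain a reading rule. It is not in the documents, so whether sites in practice lack a rule cannot be settled. This limits the conclusion to the protocol's own text. It does not cure an express exemption in that text.

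**Intent of footnote g.** Its presence on Cycle 3 Days 8 and 22, when no plamotamab is given, suggests that the authors meant review before whatever infusion is due. That is a fair reading of intent. As written, the footnote does nothing on those days.

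**Cycle 1 Day 1.** A CBC is scheduled on Day -1, Table 9 marks inpatient status from that day, and screening data have been reviewed. The gap there is literal more than practical.

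**Small consequence.** Apart from Cycle 1 Day 1, plamotamab is protected by g. Lenalidomide is taken in the evening. Total white count and platelets are still reviewed. A total white count below 500/µL would itself reveal a neutrophil count below 500/µL, although a higher one does not exclude it. After a neutropenia hold Table 8 resumes tafasitamab at the same dose, so what is missed is a delay, not a dose reduction. All of this stands, and it lowers the severity.

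**Conclusion.** The text is wrong as written, with minor severity. Section 7.6.1 exempts a count on which Table 8 withholds all three drugs, and footnote g closes the gap only for plamotamab. For a subject not on a neutropenia hold, 12 tafasitamab infusions in Cycles 1 to 3, and 30 through Cycle 12 if treatment lasts that long, have no routine reading rule in the protocol itself. The exposure falls mainly on tafasitamab.

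The totals rest on the Table 9 schedule and on a literal reading of 7.6.1 and footnote g. They do not depend on the Cycle 2 plamotamab frequency or on the 2 h gap.

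A reader might take the 12 or 30 as a number of unsafe doses. The documents do not support that: they give no rate of hold-level neutropenia, and a site may read the count without being told to. Practical reach was also limited. The protocol was to be revised before Part 2 (Section 4.1.2), and the SAP (Section 1) reports early termination with 3 subjects enrolled.

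**What to change.** Use one rule in both places.

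- **Section 7.6.1:** state that safety laboratory values, including the absolute neutrophil count but excepting the other differential components, fibrinogen, coagulation panel and urinalysis, should be reviewed before the first study drug infusion of the day.
- **Table 9, footnote g:** require results to be available and reviewed before the first study drug infusion of the day, and apply the footnote to the Cycle 1 Day 1 CBC cell, allowing the Day -1 result to be used.

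The Table 8 thresholds stay with the clinical team. The change does not reach the Day -4 priming dose, for which no CBC is scheduled.

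The cost is one sentence, one footnote and one table marker. No new sample is needed in the treatment cycles, because a CBC with differential is already scheduled on every tafasitamab day counted above. The downside is an occasional wait for the count before tafasitamab, reduced by the day-before draw that 7.6.1 and footnote g already allow.

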7.6.2. End of Treatment Visit

Subjects will have their EOT visit at the end of the last cycle of treatment. If a subject terminates before the end of a cycle, the EOT assessments (as indicated in Table 9) will be performed as early as possible after study drug discontinuation. Subjects who complete a tumor assessment within 14 days of EOT do not have to repeat the EOT tumor assessment.

